- What is the effect of difelikefalin on CKD-associated pruritus in patients on maintenance hemodialysis?

3.2 Research hypothesis:

- Difelikefalin effectively reduces CKD–associated pruritus in maintenance hemodialysis patients.

4. Objectives

4.1 General objective:

- To evaluate the effect of difelikefalin in CKD-associated pruritus on maintenance hemodialysis patients.

4.2 Specific objectives:

- I. To determine the baseline scores of the WINRS scale and Skindex-10 scale in CKD-associated pruritus on maintenance hemodialysis patients..
- II. To estimate and compare the changes in the WINRS scale, and Skindex-10 Scale between the experimental and control groups.
- III. To assess the tolerability and detect any adverse effect of Difelikefalin in patients with CKD-associated pruritus on maintenance hemodialysis throughout the study period.

5. Materials and method:

5.1. Type of study: Randomized, placebo-controlled, double-blinded trial,

5.2 Place of Study: Department of Nephrology, Chittagong Medical College Hospital, Chattogram, Bangladesh.

5.3 Study period: One and half years from acceptance of protocol.

5.4 Study population: Adult CKD stage-5 patients on MHD in the dialysis unit of the Department of Nephrology, CMCH during the study period.

5.5 Study groups: Based on the interventions, there will be two groups in the study

I. Experimental group:

Standard symptomatic treatment for itching + Intravenous difelikefalin

II. Control group:

Standard symptomatic treatment for itching + Placebo

5.6 Sampling technique: Consecutive sampling. From the Selected participants, the intervention and control will be randomly assigned in a 1:1 ratio (block size of four) through computer-generated randomization.

5.7. Inclusion criteria:

- i. Adults aged ≥ 18 years.
- ii. Patient with chronic kidney disease on HD for ≥ 3 months.
- iii. Moderate-to-severe pruritus (WI-NRS score ≥ 4).
- iv. Able to communicate clearly with the Investigator .
- v. Willing and able to provide written informed consent prior to participating in this study.

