5.8 Exclusion criteria

- i. Known case of Primary skin disease associated with Itching.
- ii. Known case of liver disease.
- iii. Known case of iron deficiency anaemia ,hematological malignancy.
- iv. Known case of hypothyroidism & hyperthyroidism.
- v. Known case of allergic reaction to Opiates .
- vi. Pregnancy.
- vii. Drug abuse, or substance dependence.

5.9. Sample size: Sample size calculation for hypothesis testing of difference between two proportions:

$$n = \frac{p(100 - p) + q(100 - q)}{(p - q)^2} (z_{\alpha} + z_{\beta})^2$$

Where,

Z_{α} = Z value of standard normal distribution at a definite level of significance

Z_{β} = Z value of standard normal distribution at a definite level of power

p = Proportion of patients with expected outcome (response rate) in the experimental group

q = Proportion of patients with expected outcome (response rate) in the control group

Here,

Z_{α} = 1.96 at 95% Confidence Interval

Z_{β} = 1.63 at 95 % power

p = 64% (Fishbane et al., 2020b)

q = 29% (Fishbane et al., 2020b)

So,

$$n = \frac{64(100.0 - 64) + 29(100.0 - 29)}{(64 - 29)^2} (1.96 + 1.63)^2 \approx 46$$

Considering 10% lost to follow-up final sample will be

$$(46 + 46 \times 10\%) \approx 50.6 \approx 51$$

That means 51 patients in each group will be needed in each group to test the hypothesis.

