Safety will be evaluated by monitoring adverse events, vital signs, clinical laboratory measurements in both group.

5.13. Data analysis:

Data will be entered into an Excel sheet to generate the master sheet. After completion of data collection, master sheet will be fed into SPSS (Windows version 27.0) for analysis. This study has two types of data: Categorical and quantitative data. Kolmogorov–Smirnov (K-S) test will be used to determine the data distribution. Finding if there is a significant difference between the data, independent samples t-test (or Mann–Whitney test in case of non-parametric data) and Chi-square test for continuous and categorical data, respectively will be used. The difference between the repeated variable in distinct visits using repeated ANOVA with the change from baseline in the weekly mean WI-NRS scale, Skindex 10 Scale. The adjusted mean difference between the groups and its two-sided 95% CI will be presented. A p -value < 0.05 will be considered significance.

5.14. Expected outcomes: Difelikefalin will significantly reduce pruritus severity compared to placebo. Participants receiving difelikefalin will report improvements in quality of life and will exhibit a favorable safety profile, with no major adverse events.

5.15. The utilization of results: This trial will provide critical evidence on the effectiveness and safety of difelikefalin in a resource-limited setting, addressing a significant unmet need in the management of CKD-aP. If proven effective, difelikefalin could become a standard treatment option for CKDaP and improve the quality of life for hemodialysis patients in Bangladesh and similar populations globally. Efforts will also be made to present these results at conferences and publish them in peer-reviewed national and international journals. The results and observations of the study will be published as a thesis and submitted to the respective university as a part of the requirement for the MD (Nephrology) Phase B examination purpose. The results of the study will be presented to the Department of Nephrology, CMCH.

[figure not shown]

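### A non-significant chi-square test, or no major events among 51 treated patients, cannot by itself support the safety wording in sections 5.14 and 5.15

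*Protocol*

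**What the plan says.** - **Objective.** Safety is specific objective III in section 4.2: "To assess the tolerability and detect any adverse effect of Difelikefalin".
- **Data.** The case record form scores each listed adverse effect (nausea, vomiting, dizziness, falls and so on) as no or yes at 3 and 6 weeks. These are categorical data.
- **Analysis.** For categorical data, section 5.13 offers only this: "Chi-square test for continuous and categorical data, respectively will be used". The threshold is a p "value < 0.05 will be considered significance". The only interval estimate it commits to is this: "The adjusted mean difference between the groups and its two-sided 95% CI will be presented". That is an interval for means and does not apply to adverse-event proportions.
- **Size.** Section 5.9 derives the sample size from response rates of 64% and 29%. Nothing is calculated for safety.
- **Claim.** Section 5.14 forecasts that treated patients "will exhibit a favorable safety profile, with no major adverse events". Section 5.15 adds: "This trial will provide critical evidence on the effectiveness and safety of difelikefalin in a resource-limited setting". Neither section says what would count as favorable or as major.

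**The concern.** The protocol fixes a significance test for the adverse-effect items and separately forecasts a reassuring safety conclusion. It gives nothing that links the two: no margin, no interval for a difference in proportions, and no upper bound when no event is seen. The results most easily read as confirming the forecast are a p-value above 0.05 and an empty row for major events.

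Both are weak evidence at this size. A p-value above 0.05 says that a difference was not shown; it does not say how large an excess remains possible. A zero count in a small arm has a non-trivial upper limit. A moderate real excess of, say, dizziness or falls could therefore be reported as no difference between the arms, while the data were still compatible with an excess that a clinician would want to know about.

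**Working it through.** **Inputs from the protocol.** Section 5.9: p = 64%, q = 29%, Z for alpha "1.96 at 95% Confidence Interval", Z for beta "1.63 at 95 % power", 10% loss to follow-up. Section 5.6: 1:1 allocation. Section 5.13: chi-square test at 0.05.

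**Input that is assumed.** The protocol gives no adverse-event rates. The control rates of 5%, 10% and 15% and the treated rates below are illustrative, and a range is shown.

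**Step 1. The plan's own figure.** n = [64×36 + 29×71]/35² × (1.96 + 1.63)² = (4363/1225) × 12.888 = 45.9, so 46; then 46 × 1.10 = 50.6, so 51 per arm. Both figures reproduce. They concern response rate only.

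**Step 2. How often the chi-square test misses an excess.** For each pair of true rates, all outcomes (x, y) with x, y = 0 to 51 are enumerated with their binomial probabilities. Power is the total probability of outcomes where |z| > 1.96, with z = [(x − y)/51] / √[2p̄(1 − p̄)/51] and p̄ = (x + y)/102 (the uncorrected chi-square). The miss rate is 1 − power.

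| Control vs treated | Ratio | Missed |
|---|---|---|
| 5% vs 10% | 2 | 85% |
| 10% vs 20% | 2 | 71% |
| 15% vs 30% | 2 | 55% |
| 5% vs 15% | 3 | 61% |
| 10% vs 25% | 2.5 | 48% |
| 5% vs 20% | 4 | 34% |
| 10% vs 30% | 3 | 27% |
| 5% vs 25% | 5 | 16% |

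For 80% power, the normal-approximation formula needs about 435 per arm for 5% vs 10%, 199 for 10% vs 20% and 141 for 5% vs 15%.

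**Step 3. What a non-significant result leaves open.** Take 8/51 treated against 3/51 control. Chi-square = 102 × (8×48 − 3×43)² / (51 × 51 × 11 × 91) = 2.55, p = 0.11. The risk difference is 15.7% − 5.9% = 9.8 points. The Wilson intervals are 8.2% to 28.0% and 2.0% to 15.9%. Newcombe's limits are:

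- lower: 9.8 − √[(15.7 − 8.2)² + (15.9 − 5.9)²] = −2.7 points (from unrounded values)
- upper: 9.8 + √[(28.0 − 15.7)² + (5.9 − 2.0)²] = +22.7 points (from unrounded values)

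The test reports no significant difference. The interval shows that an excess of more than 20 points is not excluded.

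**Step 4. What zero events leaves open.** With 0/51, the upper end of the exact two-sided 95% interval is 1 − 0.025^(1/51) = 7.0%. The one-sided 95% limit is 1 − 0.05^(1/51) = 5.7%. With 46 patients the two-sided figure is 7.7%. The chance of seeing no event in 51 patients is (1 − r)^51: 60% at a true rate r of 1%, 36% at 2% and 7% at 5%. It exceeds one half only when r is below 1 − 0.5^(1/51) = 1.35%.

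**The case against.** Several points on the other side are sound and limit what can be said.

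- **Section 5.14 is a forecast.** It stands under expected outcomes, next to an equally hopeful efficacy forecast. A reader might infer that the protocol treats p > 0.05 as proof of safety; it nowhere says so.
- **The test and the zero count are not the only safety information.** Section 5.12 also names vital signs and laboratory values, section 5.16 describes unblinded safety monitoring, and the data and safety monitoring plan lists severity, relatedness, action and outcome for each event. It would go too far to say that the safety conclusion can rest only on a non-significant test or an empty row. Even so, the case record form has no vital-sign field, and the monitoring table is a listing without a between-arm estimate, so these sources do not supply the missing precision.
- **Harm is not missed most of the time in general.** A reader might infer that from the doublings. It fails for 5% vs 20%, 10% vs 30% and 5% vs 25%, and on the zero-event side for any true rate above about 1.35%.
- **The uptake statement in section 5.15 depends on efficacy.** A reader might infer that a null safety test would be used to promote the drug as routine care. The protocol makes that step conditional on effectiveness.
- **Analysis detail may sit in a statistical analysis plan that is not shown, and sizing on efficacy alone is ordinary.** Both are true. The point here is narrower: the protocol itself states a significance-test rule that covers adverse effects, and itself makes safety statements that such a rule cannot carry at this size.

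**Conclusion.** The point holds in limited form. With 51 per arm, a non-significant chi-square test, or the absence of major events, cannot by itself support the forecast in section 5.14 or the strength of the safety wording in section 5.15. Under the assumed rates, the test misses a doubling from 5% or 10% in 71% to 85% of trials and misses 5% vs 15% in 61%, while larger excesses are usually detected. No major events in 51 treated patients still leaves rates up to 7.0% compatible with the data (two-sided 95%; 5.7% one-sided).

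The miss rates rest on assumed adverse-event rates, on full follow-up of 51 per arm and on the uncorrected chi-square test. The zero-event limits need only the arm size. Efficacy sizing is not affected. The change is worth making before the analysis because it costs almost nothing and prevents a null test from being reported as reassurance.

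**What to change.** - **Section 5.13.** For adverse events, replace reliance on the chi-square p-value with the number and percentage of patients per arm for each listed event, and the risk difference with a two-sided 95% confidence interval (for example Newcombe's). Where no event is seen, give the upper end of the exact two-sided 95% interval and name the convention, since the one-sided limit differs (5.7% against 7.0% for 0/51). State that a non-significant difference will not be read as evidence of safety.
- **Sections 5.14 and 5.15.** Limit the safety wording to a description over 6 weeks together with its precision, for example that zero events in 51 treated patients excludes only rates above about 7%.

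Objective III can stay as it is. The cost is a few sentences and a few extra intervals, with no additional patients or data. The downside is a more modest safety claim.

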Appendix
Case record form

Protocol Title: “Effect of Difelikefalin on CKD-Associated Pruritus in Patients on Maintenance Hemodialysis: A Randomized, Placebo-Controlled Trial”

Patient’s identification			
1	Patient ID No.		
2	Patient name :		
3	Adress		
4	Contact no:		
5	Study group	Experimental=1 Control=2	
Demographic characteristics			
1	Age:years	
2	Sex:	0=Female 1=Male	
Clinical characteristics			
1	Duration of HDMonths/years	
2	Duration of pruritusMonths/years	
3	Etiology of CKD	1=HTN 2=DM 3=GN 4=Others	
4	Baseline use of antipruritic medication	Anti histamin- Others-	
5	Online Kt/V		
Biochemical			
1	Calcium(mmol/l)		
2	Phosphate(mmol/l)		
3	PTH(pg/ml)		

	Follow-up data	Baseline	At 3-wk	At 6-wk
1	WI-NRS score			
2	Skindex-10 scale total score			

	Adverse Effect		3 weeks	6weeks
1	Nausea	N0= 0 Yes= 1		
2	Vomiting	N0= 0 Yes= 1		
3	Dizziness	N0= 0 Yes= 1		
4	Abdominal pain	N0= 0 Yes= 1		
5	Muscle spasm	N0= 0 Yes= 1		
6	Fall	N0= 0 Yes= 1		
7	Withdrawal	N0= 0 Yes= 1		
8	Expired	N0= 0 Yes= 1		
9	Others	N0= 0 Yes= 1		

	Complete the study per the Protocol 0= No 1= yes
	If not reason for drop-out 1. Adverse experience 2. Failure to return for follow-up 3. Patients refuse treatment 4. Patient died 5. Non-co-operation 6. Insufficient therapeutic response

Signature of the researcher:

Signature of the Guide/Co-guide

A. Worst Itching Intensity Numerical Rating Scale

INSTRUCTIONS

Please indicate the intensity of the **WORST ITCHING** you experienced over the past 24 hours by marking the box with the number that best describes it. After completing the scale below, please provide your initials in the **SUBJECT INITIALS** box indicating that you completed the scale by yourself and the **DATE** and **TIME** you completed the scale.

Worst Itching Over the Past 24 Hours

Please indicate the intensity of the **WORST ITCHING** you experienced over the past 24 hours.

0	1	2	3	4	5	6	7	8	9	10
										
NO ITCHING					WORST ITCHING IMAGINABLE					

B. Skindex-10 Scale

INSTRUCTIONS: During the past WEEK , how often have you been bothered by:							
	0 (Never bothered)	1	2	3	4	5	6 (Always bothered)
1. Your itching							
2. The persistence/reoccurrence of your itching							
3. The appearance of your skin from scratching							
4. Frustration about your itching							
5. Being annoyed about your itching							
6. Feeling depressed about your itching							
7. Feeling embarrassed about your itching							
8. The effects of your itching on your interactions with others (for example: interactions with family, friends, close relationships, etc.)							
9. The effects of your itching on your desire to be with people							
10. The effect of your itching making it hard to work or do what you enjoy							

Data and Safety Monitoring Board

Title: “Effect of Difelikefalin on CKD-Associated Pruritus in Patients on Maintenance Hemodialysis: A Randomized, Placebo-Controlled Trial”

Name of the researcher: This study is being conducted by [name], [name] (Nephrology), Department of Nephrology, Chittagong Medical College.

Place of the study: Department of Nephrology, Chittagong Medical College Hospital, Chattogram.

Type of Study: Randomized Controlled Trial

Members of the board:

- Professor, Department of Nephrology Chittagong Medical College and Hospital, Chattogram, Bangladesh
- Assistant professor, Department of Medicine, Chittagong Medical College and Hospital, Chattogram, Bangladesh
- Assistant professor, Department of Dermatology, Chittagong Medical College and Hospital, Chattogram, Bangladesh

DATA AND SAFETY MONITORING PLAN

Once a protocol is referred to the data and safety monitoring committee (DSMC). The first steps for the principle investigator to develop a Data and Safety Monitoring Plan (DSMP) A DSMP is a written plan that specifies a system for appropriate study oversight to ensure: (1) safety of clinical research subjects, (2) validity and integrity of research data, and (3) appropriate termination study. Once the plan elements listed here are submitted to the DSMC, the DSMC will work with the investigator to finalize the plan and assure that it is implemented.

Enrollment of the study participants by months:

Month	Approached	Eligible	Randomized	Withdrawn	Actual #	Cumulative #
1						
2						
3						
4						

Subject Status:

Patient ID	Date enrolled	Date completed	Status (Active/completed/Withdrawn)	Reason of withdrawal	Adherence	Intervention duration
1						
2						
3						
4						

Adverse events (AE) Patient ID

Patient ID	AE Onset	AE End	Severity	Related to intervention	Action taken	Outcome	Comment
1							
2							
3							
4							

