5.10. List of variables

Variables	Type	Value	Expression
Clinical			
Age	Discrete	In completed years	Mean±SD
Sex	Categorical	Male/Female	Frequency (%)
Duration of HD	Discrete	In completed years	Mean±SD
Duration of pruritus	Discrete	In completed months	Mean±SD
Cause of CKD	Categorical	GN/HTN/DM	Frequency (%)
Baseline use of antipruritic medication	Categorical	Absent/Present	Frequency (%)
WI-NRS score	Discrete	0-10	Mean±SD
Skindex-10 scale total score	Discrete	0-60	Mean±SD
Biochemical			
Calcium	Continuous	mmol/l	Mean±SD
Phosphate	Continuous	mmol/l	Mean±SD
PTH	Continuous	pg/ml	Mean±SD

Operational definitions:

- **Chronic Kidney Disease-Associated Pruritus:** CKD-aPis defined as severe and persistent itching directly related to kidney disease, without other underlying skin or systemic causes to explain the itching. (Hector alve..et al 2020)
- **MHD:** Maintenance haemodialysis was defined as regular haemodialysis treatment for at least 3 months for the management of ESKD.(Mambap, A.T., Che, I.A., Mahamat, M. *et al.* 2022)
- **Skindex-10:** The Skindex-10 scale was developed specifically for uremic pruritus and measures the weekly effect of itch across three domains (disease, mood and emotional distress, and social functioning) Scores on the Skindex-10 scale range from 0 to 60, with higher scores indicating worse itch-related quality of life. (Mathur et al., 2010).
- **Moderate-to-severe pruritus** will be defined as a mean score of >4 points on the 24-hour WI-NRS score calculated.Itching severity scores have been categorized in the literature as mild (<4), moderate (≥ 4 to <7), or severe (≥ 7) (Reich et al., 2012).
- **Efficacy outcomes:** The primary efficacy outcome will be the percentage of patients who will have an improvement (decrease) of at least 3 points from baseline at week 6 in the weekly mean score on the daily WI-NRS (Fishbane et al., 2020). The prespecified secondary efficacy outcomes will be the mean change from baseline at week 6 in the Skindex-10 scale total score (Fishbane et al., 2020).
- **Standard Symptomatic Treatment for Itching:** Standard Symptomatic treatment using antihistamin is useful. Gabapentin or Pregabalin UVB therapy ,oral charcoal or nalfuralfine might be the next line of therapy.(Mettang and kremer 2014)

5.11. Data collection instrument: A structured pretested case record form.

5.12. Data collection procedure:

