Baseline assessment: CKD patients in HD will be screened consecutively and prospectively by the above inclusion and exclusion criteria to select eligible patients. Eligible patients and their legal relatives will then fully explain the study protocol, their role in the study, and the risks of the study. They will be informed of their right to withdraw from the study at any stage. After getting written informed consent, they will be finally enrolled in the study. Detailed history clinical examination and relevant investigation will be done. Baseline demographic, clinical and biochemical information will be collected from the patients using the case record form and the scales. Blood samples will be collected after an overnight fasting period, with all aseptic precaution 5 mL of venous blood drawn into appropriate vacutainers. iPTH will be measured using a chemiluminescence immunoassay (CLIA). Serum calcium and phosphate will be analyzed using colorimetric methods on a Beckman Coulter AU480 or equivalent validated clinical chemistry analyzer.

Allocation: Once a participant is enrolled in the study and consents to participate, they will be assigned to a treatment group according to the randomization sequence. This assignment will be done immediately after the baseline assessment to ensure that it is truly random. Patients will be randomly assigned to either experimental group or placebo group with a 1:1 allocation. Randomization will be carried out using online software (Research Randomizer Version 4.0 at <https://www.randomizer.org>).

Blinding: The study will be conducted as a double-blind trial, meaning that both the participants and the investigators will be unaware of the treatment assignments.

Interventions:

In the experimental group:

Standard symptomatic treatment for itching + Difelikefalin Dose : 0.5 µg per kilogram of weight after each dialysis session.

Duration: 6 wks

In the control group:

Standard symptomatic treatment for itching + Placebo

Duration: 6 wks

Follow-up:

- i. At the end 3 wks by- WI-NRS scale, Skindex 10 scale & Adverse events
- ii. At the End of 6 wks: WI-NRS scale, Skindex 10 scale & Adverse events

During the 6-week intervention period, patients will report their worst itching intensity using the WI-NRS, and their quality of life will be assessed using the Skindex-10 questionnaire at prespecified follow-up intervals throughout the 6-week period.

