5.16. Ethical implication: Voluntary written consent will be taken from the patient/and legal guardians. All measures will be taken to protect anonymity. The interviews of the patient, clinical examination and investigations will be performed at the respective hospital after explaining the nature and purpose of the study to them, assuring that the information given by them will be used for the interest of the community and that the particulars of the patients will not be disclosed anyway. An independent safety monitoring committee conducted unblinded monitoring of patient safety throughout the trial. The trial protocol will be approved by the Ethical Review Committee of Chittagong Medical College.

Schedule:

Time Schedule (GANTT CHART)

	1 st	2 nd	3 rd	4 th	5 th -6 th	7 th -18 th	19 th - 21 th	22 th - 23 th	24 th
Problem definition									
Literature review									
Research design									
IRB clearance									
Data collection									
Data analysis									
Report writing									
Submission									

5.17 Study flow chart:

5.18 References:

- Brennan, F., 2024. The Pathogenesis of CKD–Associated Pruritus (CKD-aP): A Theoretical Model and Relevance for Treatment. *Kidney360*, pp.10-34067.
- Brennan F. Emerging insights into the mechanisms of CKD-associated pruritus. *JNephrol Res*. 2024;12(1):15–22.

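### The protocol says investigators will not know the treatment assignment, but the case record form the researcher signs has a field for the actual arm

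*Protocol*

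**What the plan says.** Section 5.1 describes a "Randomized, placebo-controlled, double-blinded trial". Section 5.12, under Blinding, says that "both the participants and the investigators will be unaware of the treatment assignments".

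Section 5.11 names the data collection instrument: "A structured pretested case record form". In the Appendix, item 5 of that form's patient identification block is the study group, coded "Experimental=1 Control=2". The form goes on to record WI-NRS and Skindex-10 totals at baseline, week 3 and week 6, adverse effects at weeks 3 and 6, completion status and the reason for drop-out. It ends with lines for the "Signature of the researcher" and for the guide or co-guide.

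Two further statements bear on the point. Section 5.6 has patients "randomly assigned in a 1:1 ratio (block size of four) through computer-generated randomization". Section 5.16 states: "An independent safety monitoring committee conducted unblinded monitoring of patient safety throughout the trial". The board listed at the end of the protocol has three members, one of them "Professor, Department of Nephrology Chittagong Medical College and Hospital, Chattogram, Bangladesh".

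**The concern.** The form codes real arms. They are not masked labels or kit numbers. It is also the working record on which follow-up is entered and which the researcher signs. A researcher who fills in every item knows the arm from the moment item 5 is completed, and section 5.12 rules that out.

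The outcomes are subjective, so the placebo comparison depends on the blind. A researcher who knows the arms could influence several things without ever rating itch:

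- which patient is enrolled next;
- the background antipruritic treatment, which both arms receive and which section 5.10 defines loosely, with several next-line options;
- how patients are prompted when they complete the scales;
- whether an adverse event is judged related to treatment, a column in the safety monitoring tables;
- how a drop-out is coded, since the listed reasons include lack of response.

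**Working it through.** The plan gives no figure on this point to reproduce. The main check is a comparison of the text, followed by a short calculation for the block size.

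**Step 1. Blinding statement against form.**

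| Place | What it implies |
|---|---|
| Section 5.12, Blinding | Investigators do not know the arm |
| Section 5.11 | The case record form is the collection instrument |
| Appendix, form item 5 | The actual arm is recorded with the patient identifiers |
| Appendix, rest of form | Follow-up scores, adverse effects and drop-out reason are on the same form |
| Appendix, signature lines | The researcher and the guide or co-guide sign it |

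The first row and the other four can both hold only if item 5 is masked, completed by someone else, or left blank until unblinding.

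**Step 2. Does any section supply one of these conditions?** Section 5.12, under Allocation, places assignment straight after the baseline assessment and uses a public online randomiser. It names no holder of the sequence. Section 5.13 describes entry into a spreadsheet and then SPSS, and does not say when the arm is added. No section mentions a masked code, an unblinded third party or a code-break step. The contradiction is therefore unresolved in the text.

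**Step 3. What the block size adds if past arms are visible.** The input is a 1:1 allocation in blocks of four (section 5.6). The six equally likely orders are AABB, BBAA, ABAB, ABBA, BAAB and BABA.

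- Assignments fixed by the earlier ones: AABB and BBAA have two each (third and fourth places); the other four orders have one each (fourth place). The total is 2 × 2 + 4 × 1 = 8 of 6 × 4 = 24 places, or 33.3%.
- Chance that the best guess is right, by place: first 1/2; second 2/3; third (1/3 × 1) + (2/3 × 1/2) = 2/3; fourth 1. The mean is (1/2 + 2/3 + 2/3 + 1)/4 = 2.833/4 = 70.8%, against 50% when past arms are concealed.
- With 102 patients, 102/4 = 25.5, so there are 25 complete blocks. On average 25 × 4/3 = 33.3 of the first 100 assignments would be known in advance.

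These figures apply only if every earlier arm is known in order. Under an intact blind the block size predicts nothing.

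**The case against.** The strongest reply is that the form shows a field and signature lines, not when item 5 is completed or by whom. The analysis file needs a group variable, and section 5.13 moves data to SPSS only after collection ends. Entering the arm at that stage would fit. This stands as far as it goes: a reader might infer that the blind will in fact be broken during follow-up, and the protocol does not show that. It shows a contradiction that nobody following the form as printed could avoid.

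The second reply concerns the route of bias. A reader might infer that an unblinded researcher would be scoring the primary outcome. The WI-NRS sheet has patients initial that they completed it themselves, and the form field does not unblind patients. That reply stands, and only the indirect routes remain. The document also gives no basis for expressing the bias in WI-NRS points.

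The third concerns the safety board. A reader might infer that unblinded data reach the department running the trial. The text does not support this. Unblinded safety boards are normal, and the board's template tables have no treatment-arm column. Nothing says that the Nephrology member treats or assesses trial patients or passes on data. It is also an assumption that the committee in section 5.16 is the board listed at the end, although no other is described. What remains is a narrow gap: the committee is called independent, one member comes from the trial's own department, and no separation from trial staff is described.

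**Conclusion.** The protocol contradicts itself on blinding, and the contradiction should be removed before the first patient is randomised, because an unblinding cannot be reversed. The conclusion rests on the form being completed as printed; no section says otherwise. The resulting bias would be indirect, and the document does not allow its size to be bounded.

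Two minor notes follow. The fixed block of four is not a separate fault, because it makes 33.3% of assignments certain and the best guess 70.8% correct only if past arms are visible. The board's membership raises a question of stated independence and is not evidence of a leak.

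**What to change.** 1. Replace item 5 of the case record form with a randomisation or kit number.
2. State in section 5.12 that the code list is held by a named role already on site that neither enrols nor assesses patients, and that arm codes are merged with the data only after data collection is closed.
3. Keep the block size out of documents that investigators hold. Varying the block size adds little once the form is corrected.
4. State in section 5.16 or the safety monitoring plan that arm-level data seen by the committee are not shared with trial staff.

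The cost is one form edit, a few sentences of protocol text and some time from the person holding the list, for which the budget has no separate line. No extra patients, visits or measurements are needed. If item 5 was always meant to be completed after unblinding, the minimum change is one sentence on the form saying so, but a coded number is safer because it does not depend on the field being left blank.
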